7.2 PARTICIPANT DISCONTINUATION/WITHDRAWAL FROM THE STUDY

Participants are free to withdraw from participation in the study at any time upon request. An investigator may discontinue a participant from the study for the following reasons:

- Any event or medical condition or situation occurs such that continued collection of follow-up study data would not be in the best interest of the participant or might require an additional treatment that would confound the interpretation of the study
- The participant meets an exclusion criterion (either newly developed or not previously recognized) that precludes further study participation

The reason for participant discontinuation from the study will be recorded on the Case Report Form (CRF) accessed through the data management platform. Participants who sign the informed consent form and are randomized but do not receive the study intervention may be replaced. Participants who sign the informed consent form, and are randomized and receive the study intervention, and subsequently withdraw, or are discontinued from the study, will not be replaced.

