5.2 EXCLUSION CRITERIA

An individual who meets any of the following criteria will be excluded from participation in this study:

- 1. Participants who are pregnant
- 2. Participants who are caregivers (e.g., mothers or fathers) of infants (< 3 months of age) or of adults who require care at night
- Participants who are deemed unable to complete the study protocol as a result of cognitive impairment, severe medical (i.e., unstable epilepsy or seizure disorder, treatment for cancer or congestive heart failure, or a condition that may require hospitalizations, surgery, or new treatments during the study period) or severe mental illness (schizophrenia, psychosis, bipolar I disorder), or active substance use disorder
- 4. Participation in another treatment or intervention study that would interfere with the current study within the time period beginning from initial baseline assessment until the 6-month follow-up assessment
- 5. Participation in regular night shift work more than 1x/ week
- 6. Patients with severe excessive daytime sleepiness ESS>=16
- 7. Patients with self-reported previous diagnosis of untreated moderate-to-severe obstructive sleep apnea
- 8. Patients with self-reported or health professional diagnosis of narcolepsy
- 9. Patients who have received specialty behavioral treatment for insomnia within the past 3 months
- 10. Change in prescribed depression medications within the past 3 months
- 11. Change in prescribed insomnia medications (e.g., hypnotics) within the past 1 month, or use of a sedative hypnotic beyond the max therapeutic dose

18 May 2022

- 12. Unavailable for follow-up during the study period (e.g., plan to leave the country for an extended period of time without access to internet)
- 13. Absence of primary care provider consent for patient participation
- 14. Patients with non-standard sleep patterns (bedtimes outside of 8pm-2am or awakenings outside of 4am-10am)
- 15. Patients who have full-time transportation and moving occupations (e.g., full-time motor vehicle operators, drivers [e.g., Ubers, Lyfts, taxis, trucks], pilots)

Children under 18 years will not be included in the study. They will not be included as chronic insomnia is much less common in children than in adults.

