5.3 LIFESTYLE CONSIDERATIONS

During this study, participants are asked to:

- Refrain from starting specialty behavioral treatment or pharmacotherapy for insomnia.
- Should not be planning on becoming pregnant in the 8-month duration of the study.
- Remain available during the study period, and as such should refrain from leaving the country for an extended period of time

If a participant has used prohibited medications, if they become pregnant during the study duration, or leave the country for extended periods of time, that will result in early study intervention discontinuation by the study investigator.

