7.1 DISCONTINUATION OF STUDY INTERVENTION/EXPERIMENTAL MANIPULATION

When a participant discontinues from Somryst but not from the study, remaining study procedures will be completed as indicated by the study protocol. If a clinically significant finding is identified (including, but not limited to changes from baseline) after enrollment, the investigator or qualified designee will determine if any change in participant management is needed. Any new clinically relevant finding will be reported as an adverse event (AE).

The data to be collected at the time of study intervention discontinuation will include the following:

- The reason(s) for discontinuing the participant from the intervention, and methods for determining the need to discontinue
- If the participant is due to complete assessments within 2 weeks of being discontinued from the study intervention, those assessments will be administered at the time of discontinuation; if the next scheduled assessments are more than 2 weeks from the discontinuation date, the discontinued participant will wait for the next scheduled assessment. Thereafter, the participant will be included in all future scheduled assessments, even though not participating in the intervention.

18 May 2022

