8.3.8 EVENTS OF SPECIAL INTEREST N/A

8.3.9 REPORTING OF PREGNANCY

Pregnancy is not reported as an adverse event. In the event of a pregnancy during trial participant, participants will be asked to discontinue the study intervention.

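### Section 7.2 may end follow-up when a confounding treatment is needed, overlapping with 5.3, 7.1, 8.3.9 and 9.4.2; it should state that ISI collection continues in both arms

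*Combined protocol and SAP*

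**What the plan says.** Section 7.2 governs leaving the study. It is permissive: "An investigator may discontinue a participant from the study for the following reasons". The first ground covers an event, condition or situation in which continuing to collect follow-up data is against the participant's interest, or which "might require an additional treatment that would confound the interpretation of the study". The second ground is: "The participant meets an exclusion criterion (either newly developed or not previously recognized) that precludes further study participation". Section 7.2 requires the reason to be recorded but provides for no later assessment.

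Other sections deal with overlapping events at the level of the intervention:

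- Section 5.3: "If a participant has used prohibited medications, if they become pregnant during the study duration", or on extended absence from the country, "that will result in early study intervention discontinuation by the study investigator".
- Section 8.3.9, on pregnancy: "participants will be asked to discontinue the study intervention". Pregnancy is also the first exclusion criterion in 5.2 ("Participants who are pregnant").
- Section 7.1, for someone who stops Somryst but stays in the study: "Thereafter, the participant will be included in all future scheduled assessments, even though not participating in the intervention".
- Section 9.4.2 (Missing Data): key outcomes are still sought from patients who drop out of the intervention.

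Section 6.5 bars starting specialized behavioral treatment or drug treatment for insomnia during the study, while 6.1.1 describes usual care in the control arm as possibly including drug treatment. Section 6.1.1 also puts controls on the same assessment schedule as the intervention arm.

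**The concern.** A participant who starts, or appears to need, a sleep medication can be handled in two ways. Under 5.3 with 7.1, the intervention stops and ISI is still measured. Under 7.2, the investigator may end study participation and the later ISI is never collected. The choice is left to discretion, without a criterion.

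The reason for removal matters because needing more treatment is plausibly a sign of how the insomnia is going. The mixed model in 9.4.2 is described as robust for data missing at random. Intent-to-treat (9.3) keeps the patient in the model through ISI values already observed, but it cannot supply a 9-week or 6-month value that was not taken.

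Removal could also differ by arm. Section 7.1 names Somryst. A control patient has no Somryst to stop, so no sentence says explicitly that a control who starts insomnia treatment continues to be assessed.

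Finally, the plan needs these patients. Table 1 records sleep medicines at 9 weeks and 6 months, and 9.4.9 compares the arms on starting or using sleep medication and repeats the analysis without users. Ending follow-up for those who start medication removes the data for both.

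**Working it through.** **Step 1: the sections side by side.**

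| Event | Section 7.2 | Other sections |
|---|---|---|
| New insomnia medication or treatment | First ground: participant may leave the study | 5.3: prohibited medication leads to intervention discontinuation; 7.1 (Somryst) and 9.4.2: outcomes still collected |
| Pregnancy | Not an additional-treatment event; may fall under the second ground, as exclusion criterion 1 | 5.3 and 8.3.9: intervention discontinued; 7.1: assessments continue |
| Control patient starts insomnia treatment | First ground applies as for Somryst | 6.1.1: same assessment schedule; 7.1 does not mention controls |

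No section gives an order of precedence.

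**Step 2: the plan's own figure.** Section 9.2 gives 90% power for 3 ISI points with SD of change 6.0, two-sided 0.05, 200 randomized and 170 followed (85 per arm).

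- Standard error = 6 × √(2/85) = 0.920.
- Power = Φ(3/0.920 − 1.96) = Φ(1.30) = 90.3% (90.0% with the noncentral t). The stated figure is reproduced.
- If removals under 7.2 came on top of the 15% attrition (an assumption), power would be 88.5% with 160 followed and 86.5% with 150. Lost power is the smaller issue; the main one is bias.

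**Step 3: how large a bias could be.** The documents give no removal rate, no imbalance between arms and no link between removal and outcome, so this is illustration.

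Assumed: baseline SD 4, 9-week SD 6, correlation 1/3. The covariance is 4 × 6 × 1/3 = 8, and the SD of change is √(16 + 36 − 2 × 8) = 6.0, matching 9.2. A fraction p of one arm loses its 9-week ISI, and removal has correlation r with poor ISI change.

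- Shift in that arm's mean change among those retained: 6 × r × φ(z)/(1 − p), where z is the (1 − p) normal quantile.
- The mixed model recovers the part that baseline explains. The correlation of change with baseline is (8 − 16)/(6 × 4) = −1/3, so 1/9 is recovered and 8/9 remains.
- p = 5%: φ(1.645) = 0.1031 and 0.1031/0.95 = 0.1086. At r = 0.25, 6 × 0.25 × 0.1086 × 8/9 = 0.14. At r = 0.5 the shift is 0.29.
- p = 10%: φ(1.282) = 0.1755 and 0.1755/0.90 = 0.195. At r = 0.25, 6 × 0.25 × 0.195 × 8/9 = 0.26. At r = 0.5 the shift is 0.52.

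A simulation of the maximum-likelihood contrast (100 per arm, true effect 3.0, 4,000 runs per cell, simulation error about 0.014) agrees:

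| r | p | Controls lost | Somryst lost | Equal loss |
|---|---|---|---|---|
| 0.25 | 5% | 2.84 | 3.14 | 3.01 |
| 0.25 | 10% | 2.74 | 3.27 | 3.02 |
| 0.5 | 5% | 2.71 | 3.26 | 3.01 |
| 0.5 | 10% | 2.49 | 3.49 | 3.01 |

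With no true effect, the same one-arm losses produce a false difference of about 0.14 to 0.52 points in either direction. If both arms lose patients unequally (10% and 5%), the contrast runs from 2.77 to 3.20 over the two values of r.

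**Step 4: scale.** The shifts are 0.14/3 = 5% to 0.52/3 = 17% of the design effect. The contrast's standard error is 6 × √(2/100) = 0.85 with complete data, so each shift is below one standard error. At 85 per arm, a contrast reduced from 3.0 to 2.5 would lower power from 90.3% to 77.5%.

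**The case against.** The best defence is that Section 7 has two tiers. Section 7.1 covers people who leave Somryst but not the study, and 7.2 covers people who leave the study. The promise in 7.1 of continued assessment therefore presupposes that 7.2 has not been used. Section 7.2 says may, so follow-up need not end. That stands: a reader might infer that the sections contradict each other, and the text does not support that. It is an unresolved overlap left to discretion.

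Three other inferences also go too far:

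- That 5.3 and 8.3.9 stop only the intervention. Neither contains that limit; it comes from reading them together with 7.1.
- That pregnancy is a confounding-treatment event. It reaches 7.2 only through the second ground, which is confined to criteria that preclude further participation, and 8.3.9 gives it a specific rule. Section 7.2 does not say which criteria preclude participation, so the question stays open.
- That removal will be selective by arm. Section 6.3 leaves the principal investigator unblinded, but outcome assessors are blinded, and nothing shows that removals would be unequal.

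The plan also has safeguards. Section 9.4.2 collects reasons for dropout and who decided it, compares patients with and without missing data, and adds multiple imputation if attrition is related to other characteristics. Section 9.2 allows 15% attrition. These help describe the loss and preserve power, but they do not fully correct for values missing because of the unobserved outcome.

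**Conclusion.** The point holds as a cheap improvement. Section 7.2 permits ending ISI collection for a reason plausibly tied to the outcome, other sections would keep collecting it after overlapping events, and no text settles which applies. The gap is widest for controls, for whom 7.1 has no wording.

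Direction and size are unknown. Losing poor responders from the control arm works against Somryst, losing them from Somryst works in its favour, and equal loss roughly cancels. The range of about 0.1 to 0.5 ISI points rests on assumed values: 5% to 10% lost from one arm only, and correlation 0.25 to 0.5 between removal and poor change. If the added treatment itself lowers ISI, the shifts are smaller. A reader might infer that the primary result will be biased, or biased towards Somryst; the documents support neither. The sample size and stated power are unaffected.

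**What to change.** Amend 7.2 to say that starting or needing an additional treatment, or becoming pregnant, does not by itself end ISI collection at 9 weeks and 6 months in either arm. Keep two exceptions: withdrawal of consent, and the existing ground that continued data collection is not in the participant's best interest. Extend the continued-assessment rule in 7.1 to mEUC participants. Reconcile 7.2 with 5.3, 7.1, 8.3.9 and 9.4.2 so that one rule governs each event. This concerns data collection; clinical rules for stopping the intervention stay with the sponsor.

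The cost is a wording amendment and a few more follow-up calls. The sample size and analysis model do not change. ISI in the retained patients will also reflect the added treatment, which the sensitivity analysis in 9.4.9 excluding sleep-medication users partly addresses.

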7.3 LOST TO FOLLOW-UP

A participant will be considered lost to follow-up if he or she fails to return for 3 scheduled visits and study staff are unable to contact the participant after at least 3 attempts.

The following actions must be taken if a participant fails to return to the clinic/virtual meeting for a required study visit:

- The site will attempt to contact the participant, reschedule the missed visit within 14 days, counsel the participant on the importance of maintaining the assigned visit schedule and ascertain if the participant wishes to and/or should continue in the study
- Before a participant is deemed lost to follow-up, the investigator or designee will make every effort to regain contact with the participant (where possible, 3 telephone calls and texts, if necessary, a certified letter to the participant's last known mailing address, email, or local equivalent methods). These contact attempts will be documented in the participant's study file.

8 STUDY ASSESSMENTS AND PROCEDURES

8.1 ENDPOINT AND OTHER NON-SAFETY ASSESSMENTS

Overview:

18 May 2022

Study candidates who meet initial eligibility criteria and consent to participate will be invited for an office visit or a virtual visit where they will complete a baseline sociodemographic and psychosocial survey battery, and be asked to complete a daily sleep diary for 14 days and to wear an actigraph (Actiwatch) to capture continuous objective sleep data on sleep duration and sleep efficiency for 14 days. Participants will be asked to return their actiwatch via mail. After completing the baseline assessment, patients will be randomly assigned in a 1:1 ratio to either the Culturally Adapted Somryst intervention condition or to minimally Enhanced Usual Care (mEUC) condition. Patients in the intervention group receive digital CBT-I, usual care, and a sleep hygiene brochure. Patients will also be trained on how to record their daily sleep diaries using a smartphone diary; and will receive prompts on their smartphones or emails to remind them when to complete the daily sleep diaries. Patients randomized to the control group will receive minimally enhanced usual care, which will include usual care provided by their PCP and a sleep hygiene brochure. Patients in both groups will have their insomnia severity assessed again at a post-intervention (9 weeks) and 6-months. Patients in both groups will also wear the ActiwatchSpectrum Pro to objectively assess sleep for 2 weeks after enrollment and again for 2 weeks post-intervention (9 weeks).

All study surveys will be administered by research staff remotely via a teleconference platform or inperson dependent on participant preference.

Screening & Primary Endpoint:

All interested patients will complete a standard screening questionnaire to determine study eligibility according to severity of insomnia. Basic sociodemographic and technological literacy information will be collected. Insomnia symptoms in the past 2 weeks will be measured with the Insomnia-Severity Index (ISI) in order to assess severity of insomnia.⁸⁰ The ISI has excellent psychometric properties, and is reliable and valid in English,⁸⁰ and adapted for use in Spanish-speaking populations.⁸¹ Changes in insomnia symptoms will also serve as the primary outcome.

Baseline:

Study candidates who meet initial eligibility criteria and consent to participate will be invited to a virtual online visit where they will complete a baseline sociodemographic and psychosocial survey battery.

Secondary Outcomes:

Health-related quality of life will be assessed through the validated Short-Form 12 (SF-12), which is a 12item self-report inventory that generically measures quality of life; it yields a measure of global healthrelated wellbeing as 8 domain-specific subscores.⁸² This will be assessed at baseline and at postintervention (9 weeks) and 6-month follow-up.

Sleepiness will be measured with the 8-item Epworth Sleepiness Scale, a brief, validated self-report scale of daytime sleepiness with excellent psychometric properties.⁸³ This will be assessed at baseline and at post-intervention (9 weeks) and 6-month follow-up.

Satisfaction with care will be measured using a question adapted for this trial asking patients to rate the quality of professional care they have received for their symptoms of insomnia.⁸⁴ This will be assessed at baseline and at the post-intervention visit (9 weeks). Based on current best practices⁶⁶ of cultural adaptation of evidence-based interventions, we will also ask participants in the intervention group to

18 May 2022

rate their satisfaction with, as well as their difficulties with program content or activities after each online session.

Self-reported and actigraphy assessed wake after sleep onset and self-reported sleep onset latency will be assessed at baseline and at post-intervention for 14 days.

Sleep duration and sleep efficiency will be measured continuously and unobtrusively for 14 days following the baseline visit and post-intervention using the ActiWatch SpectrumPRO, a waterproof, lightweight, actigraphy-based device that measures physical activity continuously and can be worn for 24 hours daily. The validity of actigraphy for determining sleep duration in particular, compared with the gold standard polysomnography, is excellent.⁸⁵

Sleep quality will be measured at baseline, post-intervention, and at 6-months follow-up with The Pittsburgh Sleep Quality Index (PSQI),⁸⁶ which has excellent psychometric properties, and established validity among Spanish-speakers.⁸⁷

Other Measures: *Sociodemographic Information* will be collected at screening including, age, sex, race, country of origin, educational attainment, nativity status, household income, employment status, and health insurance status. **Direct health care costs** will consist of the retail costs of Somryst (payer's costs plus patient out-of-pocket costs). Structured interviews will gather information about health care utilization (primary care, other ambulatory care, emergency department, or hospital visits). **Indirect costs** will include patients' lost productivity due to 1) participating in Somryst sessions, and 2) lost productivity related to poor sleep quality.

8.2 SAFETY ASSESSMENTS

Safety assessments will include inquiries into experience of adverse events through semi-structured interviews during the post-intervention (9 weeks) and 6-month assessments. There will also be a creation of a Data Safety and Monitoring Board that will monitor and review adverse events and safety.

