1.3 SCHEDULE OF ACTIVITIES

After the cultural adaptation of Somryst developed in study 1, we will then enroll 200 patients into the RCT to compare the effectiveness of the culturally adapted digital program of CBT-I (Spanish Somryst) to minimally enhanced usual care and to determine cost-effectiveness of the intervention. Summary data from our pilot study indicate that 94 people were screened over 6 months, 52% were found eligible, and 71% completed the study. In particular, our screening in one primary care clinic over two months resulted in 22 people screened, 77% were eligible, and 71% completed the first focus group. Our pilot data indicate that we are able to screen 8 patients/month and enroll patients/month from one clinic and that an accrual rate of 12/month from multiple clinics is reasonable. The specific list of measures and schedules of activities are represented in Table 1.

Table 1. List of Measures and Schedule of Activities

	Screening/ Enrollment	Baseline	Pre-Tx	Treatment	Post-Tx (9 weeks)	6-mo Follow -Up
Procedure/Assessment/Follow -Up Windows	Virtual or in person	Virtual or in person	14 days before tx	Through Week 9 of Study	Post-Tx (9 weeks)	6-mo Post- Tx
Sociodemographic information	Х					
Insomnia Severity Index	Х	Х		Х	Х	Х
Informed Consent/Enrollment	Х					
Permission for Future Contact and Use	х					
Sleep and Depression Medicines	х				Х	Х
Sleep Disorder	х					
CAGE Assessment	Х					
Assessment for Bipolar/Psychosis/ Schizophrenia	Х					
Health Care Coverage	Х					
Assessment for Cognitive Impairment	Х					
Language Proficiency	х					
Technology Use	Х					
Referral/Contact Information	Х					
Randomization				Х		
Generalized Anxiety Disorder (GAD-7)		Х		Х	Х	Х
Epworth Sleepiness Scale (ESS)	Х	Х			Х	Х

			1	-	1
Pittsburgh Sleep Quality Index (PSQI)	Х			X	X
Quality of Life (SF-12)	Х			Х	Х
Satisfaction with Care (PACIC)	Х			Х	Х
Health Literacy	Х				
Penn State Worry Questionnaire (PSWQ)	X				
Personal Health Questionnaire Depression Scale (PHQ-8)	Х		х		
Health Care Utilization	Х			Х	Х
Medical History	Х				
Dysfunctional Attitudes and Beliefs about Sleep (DBAS-16)	Х			X	Х
Hospitalization				Х	Х
Acceptability and satisfaction with intervention				X	
Actigraphy		Х		Х	
Usability and Net promoter questionnaire				Xa	
Sleep Diary		Х		Х	
Adverse Events			Х	Х	Х

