8.3.4 TIME PERIOD AND FREQUENCY FOR EVENT ASSESSMENT AND FOLLOW-UP

The occurrence of an adverse event (AE) or serious adverse event (SAE) may come to the attention of study personnel during study visits and interviews of a study participant presenting for medical care, or upon review by a study monitor.

All AEs, not otherwise precluded per the protocol, will be captured on the appropriate case report form (CRF). Information to be collected includes event description, time of onset, clinician's assessment of severity, relationship to study procedures (assessed only by those with the training and authority to make a diagnosis), and time of resolution/stabilization of the event. All AEs occurring while on study will be documented appropriately regardless of relationship. All AEs will be followed to adequate resolution.

Any medical or psychiatric condition that is present at the time that the participant is screened will be considered as baseline and not reported as an AE. However, if the study participant's condition deteriorates at any time during the study, it will be recorded as an AE.

Changes in the severity of an AE will be documented to allow an assessment of the duration of the event at each level of severity to be performed. Documentation of onset and duration of each episode will be maintained for AEs characterized as intermittent.

Research Staff will record events with start dates occurring any time after informed consent is obtained until 7 (for non-serious AEs) or 30 days (for SAEs) after the last day of study participation. At each study visit, the investigator will inquire about the occurrence of AE/SAEs since the last visit. Events will be followed for outcome information until resolution or stabilization.

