9.2 SAMPLE SIZE DETERMINATION

Prior studies suggest that CBT-I yields approximately an 8-point reduction in the ISI, our primary measure of insomnia, with the standard deviation (SD) of post-intervention change scores being 4 to 5 points. Our expectation is that the improvement in patients assigned to the intervention condition (Somryst) will be 8 points or greater, and that those assigned to minimally enhanced usual care (mEUC) will exhibit a 5-point improvement. Typically, we expect the SD of change scores to increase for longer intervals (e.g., 6 or 12 months), and have therefore conservatively based our power calculations on a SD (change) of 6.0. Accordingly, randomization of 200 patients to Somryst versus mEUC (1-to-1 ratio) will provide 90% power to detect a differential reduction (post-intervention and 6-month follow-up) in ISI of 3 points or larger, using a 2-tailed Wald chi-square test of the appropriate contrast. This sample size estimate allows for up to 15% attrition, such that we have baseline data on all 200 patients (collected prior to randomization), but follow-up data on only 170.

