organization). The secondary cost-effectiveness analysis will be from the patient's point of view and include out-of-pocket medical costs and costs of lost productivity (both due to participation in Somryst sessions and due to poor sleep quality). For the main analysis from the payer's point of view, we will include cumulative CBT-I costs for the intervention arm payers and patients' combined costs to access and complete the web-based CBT-I intervention), and for both CBT-I and mEUC we will gather cumulative utilization data on medications, office visits, emergency department visits, and hospitalizations over the follow up period. We anticipate that most of these data can be gathered from EPIC the electronic health record (EHR) used in the AIM Clinic and New York Presbyterian Hospital, but participant follow up interviews will both validate electronic record data and capture any health care utilization at outside clinics and hospitals. Health facility visit costs will be entered as the reimbursement for that visit type specified by the Centers for Medicare and Medicaid Services⁹⁹ fee schedule. Mean wholesale medication prices will be estimated from the most recent "Redbook" listing of wholesale drug costs. For the secondary analysis from the patient's point of view, we will analyze data from participant interviews data on out-ofpocket medication costs, office visit co-pays, and lost compensation and missed work. Productivity losses will be estimated by multiplying age-specific labor force participation rates by average age-specific U.S. adult annual earnings for the participant's time observed in in the trial. Sources for average annual earnings (Current Population Survey 2014), labor force participation rate (Bureau of Labor Statistics, BLS), and consumption costs (BLS Consumer Expenditure Survey) were summarized in the Second Panel of Cost-Effectiveness.

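### Planned harms ascertainment ends at the last attended assessment, while ED visits and admissions to be gathered from the health record feed only the cost analysis

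*Combined protocol and SAP*

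**What the plan says.** All references are to the combined protocol and SAP.

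- **Scheduled ascertainment.** Section 8.2: "Safety assessments will include inquiries into experience of adverse events through semi-structured interviews during the post-intervention (9 weeks) and 6-month assessments". Section 8.3.4 adds: "At each study visit, the investigator will inquire about the occurrence of AE/SAEs since the last visit".
- **Unscheduled routes.** Section 8.3.4 also expects events to surface "during study visits and interviews of a study participant presenting for medical care, or upon review by a study monitor".
- **Schedule of activities (section 1.3, Table 1).** The "Adverse Events" row carries three marks. Read against neighbouring rows, they appear to fall under Treatment, Post-Tx and 6-month follow-up. The Treatment column is headed "Through Week 9 of Study". No section says who asks about adverse events in that period, or how.
- **Expected loss.** Section 9.2 allows for 15% attrition, leaving "follow-up data on only 170".
- **A second data source.** Section 9.4.3 plans to gather ED visits and hospitalizations in both arms during follow-up for the cost-effectiveness analysis. On the source it says: "We anticipate that most of these data can be gathered from EPIC the electronic health record (EHR"). Participant interviews are to validate the record and to pick up care received elsewhere.
- **Safety analysis.** Section 9.4.4 reads N/A.

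**The concern.** Hospitalization is a seriousness criterion in section 8.3.2. Section 8.3.3.3 names fatigue-related accidents as the serious events that might be related to the intervention. ED visits and admissions are where many such events would appear, and the plan already intends to gather both in each arm. Yet nothing links those data to the AE form, to the clinician's assessment under 8.3 or to the monitoring board.

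For a patient who stops attending, the plan therefore describes no systematic way to meet its own commitment in 8.3.4 to document all adverse events on study whatever their relationship to it. Only the Somryst arm receives sleep restriction (section 6.1.1), so loss linked to harm could affect the arms unequally. Timing matters too. The reporting clocks in 8.3.6 and 8.4.2 run from when the investigator learns of an event, so an admission found only when the cost file is assembled could surface long after it happened.

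**Working it through.** **1. Where the attrition figure comes from.** Inputs from 9.2 and 9.4.2: difference 3 ISI points, SD of change 6.0, two-sided alpha 0.05, power 90%, allocation 1:1, attrition 15%.

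- Patients per arm: 2 × (1.960 + 1.282)² × 6² / 3² = 84.1, rounded up to 85; total 170.
- Inflated for loss: 170 / 0.85 = 200.
- Power with 85 per arm: SE = 6 × √(2/85) = 0.920; 3 / 0.920 = 3.26; Φ(3.26 − 1.96) = 0.903 (0.900 with the noncentral t).

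The plan's figures reproduce. The allowance is 200 × 0.15 = 30 patients, or 15 per arm if loss is equal.

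**2. What zero events would rule out.** If no event is seen among n patients in an arm, the exact one-sided 95% upper limit on the risk is 1 − 0.05^(1/n).

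| Patients ascertained per arm | Upper limit |
|---|---|
| 100 (complete capture) | 2.95% |
| 85 (15% loss) | 3.46% |
| 71 (29% loss) | 4.13% |

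The 29% row uses the pilot completion of 71% in section 1.3. The pilot activity that section describes is a focus group, so this row is the far end of a range and not a forecast for the trial.

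**3. Chance of seeing at least one event in an arm.** At an assumed true risk of 1%, this is 1 − 0.99^n: 63% for n = 100, 57% for n = 85 and 51% for n = 71.

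**4. Share of events missed.** Let L be the proportion lost and k the risk in lost patients relative to retained patients. If every event in a lost patient is missed, the share missed is Lk / [(1 − L) + Lk].

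| | k = 1 | k = 2 | k = 3 |
|---|---|---|---|
| L = 15% | 15% | 26% | 35% |
| L = 29% | 29% | 45% | 55% |

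The documents give no value for k. These shares are assumption-driven upper bounds, because some lost patients will already have given partial data.

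**5. What the record could add.** The 100-patient figures assume complete capture, which the record cannot give.

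- Section 9.4.3 locates it in one clinic and the affiliated hospital, while section 4.1 recruits across a wider clinic network.
- Care elsewhere is captured only by the interviews that lost patients miss.
- An accident that leads to no visit never appears.
- Section 9.4.3 bases its main cost-effectiveness analysis on 9 weeks, so extraction to 6 months for every randomized patient is not assured by the present text.

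The 3.0% limit is therefore a best case.

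**The case against.** The strongest reply is that the plan has more safeguards than sections 8.2 and 9.4.3 alone suggest.

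- A patient lost after week 9 has already given the 9-week interview, which follows the period when sleep restriction is delivered. Table 1 also appears to mark adverse events during treatment.
- Section 8.3.4 allows detection when a participant presents for care or on monitor review, and 8.3.5 has the investigator record any event identified.
- Patients who stop Somryst stay in all later assessments (7.1). Repeated contact attempts come before loss is declared (7.3). Reasons for dropout are sought (9.4.2).

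These points stand, and they defeat several stronger readings that a reader might infer:

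- That lost patients contribute no harms data at all. They contribute none that is systematically collected after their last contact.
- That an admission in a lost patient could never reach safety review. Nothing forbids staff from logging one they see; the text only fails to require a search.
- That serious harm is selectively undercounted in the Somryst arm. This is plausible, but no section shows or predicts differential loss.
- That the record extraction already covers every randomized patient. The documents do not say so, and whether records may be searched after loss or withdrawal depends on the consent terms.

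The safeguards do not remove the core gap. The unscheduled routes are passive, Table 1's treatment-period mark has no described procedure, and a general duty to document events gives no means of finding them in people who no longer attend.

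**Conclusion.** The point holds as a modest, optional improvement. Active adverse-event ascertainment depends on attendance, up to 30 of 200 patients may have incomplete harms data, and a planned two-arm source of serious-event information has no stated link to safety.

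The measurable gain is small: with zero events in an arm, the upper limit on risk falls from 3.5% (85 patients) to 3.0% at best (100 patients). This assumes the full 15% allowance is used, equally in both arms, and that the record captures everything. Unequal undercounting by arm remains a possibility only. No sample-size or power figure changes.

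**What to change.** 1. In 8.2 and 8.3.4, state that ED visits and hospital admissions found in the record extraction or the utilization interview, for all randomized patients through 6 months and subject to consent, are entered on the AE form and assessed under 8.3.
2. Run the extraction when the 9-week and 6-month assessments fall due, so that events reach safety review promptly.
3. In 9.4.4, replace N/A with a count of these events by arm among all randomized patients, and state that the record covers in-network care only.
4. Reconcile 8.2 with Table 1 on adverse-event collection during treatment, stating who asks, how and when.

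The cost is protocol wording plus modest abstraction time, including extraction to 6 months where the cost analysis would have stopped at 9 weeks. Out-of-network events in lost patients will still be missed.
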